4.5.3. Prohibition and Restrictions

4.5.3.1. Precautions for Sexual Intercourse

Highly effective contraceptive measures for both males and females of childbearing potential must be documented in the source documents.

4.5.3.1.1. Female Subjects

In line with the Heads of Medicines Agencies (HMA)'s Clinical Trial Facilitation Group (CTFG) recommendation [3], female subjects are considered of non-childbearing potential if they meet one of the following criteria:

- No menses for 12 or more months without an alternative medical cause. A high follicle-stimulating hormone (FSH) level in the postmenopausal range may be used to confirm a postmenopausal state in women not using hormonal contraception or hormonal replacement therapy. However, in the absence of 12 months of amenorrhea, a single FSH measurement is insufficient.
- Permanently surgically sterile (bilateral oophorectomy [i.e. surgical removal of ovaries], bilateral salpingectomy, or hysterectomy [i.e. surgical removal of uterus]).

All other female subjects are considered to be of childbearing potential and are required to have a negative serum pregnancy test before treatment. They must use one of the following highly effective methods of birth control from the time of signing of the ICF, during the clinical study, and for at least 30 days after the last dose of IMP:

- Combined (estrogen- and progesterone-containing) (oral, intravaginal, transdermal) hormonal contraception associated with inhibition of ovulation plus a barrier method¹.
- Progesterone-only hormonal (oral, injectable, implantable) contraception associated with inhibition of ovulation plus a barrier method¹.
- Intrauterine device.

¹ As there are no current data available regarding potential interactions between IMP and hormonal contraceptives, female subjects who use hormonal contraception should supplement this with a barrier method (preferably male condom).

- Intrauterine hormone-releasing system.
- Bilateral tubal occlusion.
- Sexual abstinence defined as refraining from heterosexual intercourse during the entire period of risk associated with the study treatments. The reliability of sexual abstinence needs to be evaluated in relation to the duration of the clinical study and the preferred and usual lifestyle of the subject.

Periodic abstinence (e.g. calendar, symptothermal, post-ovulation methods), declaration of abstinence for the duration of a clinical study, withdrawal, spermicides only, and lactational amenorrhea method are not acceptable as methods of contraception.

In case a woman of childbearing potential has a vasectomized partner, provided that partner is the sole sexual partner of the participant and that the vasectomized partner has received medical assessment of surgical success, then she is not required to use an additional form of contraception.

Within these limits, the specific forms of contraception employed are left to the discretion of the subject, the investigator, and/or the subject's physician.

Female subjects of childbearing potential will be requested to do a monthly urine pregnancy test during the study. The monthly pregnancy test outcome must be documented on the subject diary card and at the next visit in the source and case report form (CRF). In case of a positive urine pregnancy test at home, the subject should immediately contact the clinical study center and the investigator must report this immediately, and under no circumstances later than 24 hours after being made aware.

The safety of GLPG1690 during breastfeeding is unknown. Women who are nursing are not allowed to take part in this clinical study.

Pregnant women or women planning to become pregnant during the study are not allowed to take part in this study.

4.5.3.1.2. Male Subjects

Men should be advised not to father a child while receiving treatment and must use effective contraception during and up to 90 days after treatment. Male subjects intending to father a child, should discontinue treatment with IMP and wait for at least 90 days before stopping the contraceptive measures detailed in this section.

Non-vasectomized male subjects with female partners of childbearing potential must be willing to use a condom from the time of the first dose of IMP, during the clinical study, and for at least 90 days after the last dose of IMP in addition to having their female partner use one of the following forms of contraception:

- Combined (estrogen- and progesterone-containing) (oral, intravaginal, transdermal) hormonal contraception associated with inhibition of ovulation.
- Progesterone-only hormonal (oral, injectable, implantable) contraception associated with inhibition of ovulation.
- Intrauterine device.
- Intrauterine hormone-releasing system.

Sexual abstinence defined as refraining from heterosexual intercourse during the entire period of risk associated with the study treatments is considered a highly effective contraceptive measure. The reliability of sexual abstinence needs to be evaluated in relation to the duration of the clinical study and the preferred and usual lifestyle of the subject.

Periodic abstinence (e.g. calendar, symptothermal, post-ovulation methods), declaration of abstinence for the duration of a clinical study, withdrawal, spermicides only, and lactational amenorrhea method are not acceptable methods of contraception.

In a case where the female partner of a male subject has undergone documented surgical sterilization that was performed more than 1 year before screening, then the subject is not required to use an additional form of contraception.

Vasectomized male subjects with female partners of childbearing potential are not required to use an additional form of contraception, provided that surgical sterilization has been successful (documented azoospermia by semen analysis).

Male subjects with a pregnant or breastfeeding partner should use a condom to prevent exposure through seminal fluid.

No sperm donation is allowed from the first dose of the IMP until 90 days after the last dose.

4.5.3.2. Prior and Concomitant Medications

Prior therapy

Prior therapy taken up to 12 weeks prior to and during the screening period, and pirfenidone and nintedanib taken any time prior to and during the screening period will be recorded after signing of the ICF, at Visit 1.

Concomitant therapy

Should any treatment other than the IMP be used during the course of the study, the name of the therapy, the dosage, the route, the reason for therapy, and the start and stop dates of administration must be recorded until the last visit. For subjects receiving oxygen, the volume administered per minute will also be recorded at each visit.

Concomitant therapies taken for the long-term treatment of pre-existing conditions can continue during the study, provided they are in accordance with the in- and exclusion criteria (see Sections 4.5.1 and 4.5.2, respectively). It is required that the use of these medications should have been stable from 4 weeks prior to screening and during the screening period (at the investigator's discretion). For nintedanib and pirfenidone, subjects need to have received a stable dose for at least two months prior to screening and during screening; stable being defined as the highest dose tolerated by the subject during those two months.

In case additional concomitant medication needs to be administered or dose adjustments for pre-existing conditions need to be performed during the study, the benefit-risk to the subject should be carefully assessed and consideration given to the timing of any necessary introduction of new medications.

The following therapies are prohibited during the course of the study and within 4 weeks prior to screening, because of lack of benefit or suggestion of harm in IPF: warfarin, imatinib,

ambrisentan, azathioprine, cyclophosphamide, cyclosporine A, bosentan, methotrexate, sildenafil (except occasional use), prednisone at steady dose >10 mg/day or equivalent.

If during the study, the subject's condition necessitates the use of one of the abovementioned medications (excluding high-dose steroids), the use of IMP should be interrupted until resolution or stabilization of this condition, preferably after consultation with the CRO medical monitor (as per study contact list) or sponsor's study physician (if the former is not available).

Precautions with concomitant medication known to prolong the QT interval

The use of medication known to prolong QT interval during the study needs to be based on a benefit-risk evaluation by the investigator, e.g. in the case of atrial fibrillation. In certain other situations (e.g. the initiation of macrolides or fluoroquinolones in case of a lower respiratory tract infection), when the benefit-risk evaluation necessitates the administration of medication known to or potentially prolonging QT, IMP can be interrupted as evaluated by the investigator after clinical assessment of the subject's profile, including the baseline QTcF and how this has changed over time for this specific subject. If the investigator elects to continue IMP, additional monitoring will be performed as per investigator's judgment. A non-exhaustive list of medication known to prolong QT interval is provided in [Appendix 7](#).

Precautions with other concomitant medications

At dose levels of 600 mg q.d., GLPG1690 has the potential to influence substantially the metabolism of substrates of CYP2C8 and to potentially be influenced by known strong CYP3A4/potent P-gp inducers/inhibitors.

- GLPG1690 demonstrated a strong time-dependent inhibition potential against CYP2C8-mediated metabolism. Consequently, GLPG1690 should not be used concomitantly with medications primarily or solely metabolized via CYP2C8 (see [Appendix 3](#)). For other medications involving part of their metabolism pathway via CYP2C8, caution should be applied on a case-by-case basis taking into consideration the benefit/risk ratio. Statins such as fluvastatin and pitavastatin are metabolized to some degree by CYP2C8, and need to be used with caution. Other statins such as simvastatin, lovastatin, and atorvastatin are theoretically less metabolized by CYP2C8. Monitoring of LFTs and creatine kinase is implemented during the study, and guidance to the subject aligned with guidance for statins in clinical practice is therefore strongly recommended. Loperamide is also a substrate of CYP2C8, and special caution should be applied in alignment with clinical practice.
- GLPG1690 is a substrate of CYP3A4 and P-gp, and could therefore be influenced by their respective inhibitors and inducers. GLPG1690 exposure is reduced up to 90% by the strong CYP3A4/potent P-gp inducer rifampin. As a consequence, strong inducers of CYP3A4 and/or P-gp are part of the exclusion criteria and should be avoided during the study to ensure proper exposure to GLPG1690 (see [Appendix 4](#)). For inhibition, strong CYP3A4 and dual strong 3A4 and potent P-gp inhibitors have shown that GLPG1690 exposure increased by 3 to 4 fold when coadministered therefore use of known strong CYP3A4 inhibitors and potent P-gp inhibitors is prohibited during the study (see [Appendix 5](#) and [Appendix 6](#)). Antibiotics from the macrolide therapeutic class are excluded, unless they are used for the short-term treatment of a lower respiratory tract

infection with interruption of IMP, which is restarted as soon as possible after the completion of the treatment with macrolides.

It is highly recommended that the CRO medical monitor (as per study contact list) or sponsor's study physician (if the former is not available) are consulted before the initiation of medication known to prolong QT interval, to be a CYP2C8 substrate, or to inhibit or induce P-gp/CYP3A4.

In certain situations, when the benefit-risk evaluation necessitates the administration of medication excluded from use during the study, IMP should be interrupted and restarted as soon as possible.

As a rule, inclusion of subjects with stable chronic illness on stable medications which are metabolized/transported by the abovementioned CYP/transporter enzymes should be decided on a case-by-case basis if not excluded or prohibited, taking into account the medical history, concomitant medication of the subject, the therapeutic index of the medication, and safety profile.

As indicated in the study contact list, the CRO medical monitor should be contacted, or the sponsor's study physician in case the former is not available (when deemed necessary by the investigator), specifically for medication with a narrow therapeutic index and/or a risk of (un)predictable AEs.

Rescue medication

If the subject shows a worsening of his/her IPF disease condition (e.g. acute IPF exacerbation), all treatment options are allowed at the investigator's discretion. The decision to continue the IMP should be taken on a case-by-case basis by the investigator, and in case of doubt can be discussed with the CRO medical monitor (as per study contact list) or sponsor's study physician (if the former is not available).

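### Section 4.5.3.2 of the protocol conflicts on macrolides for a lower respiratory tract infection: one paragraph lets IMP continue, another requires it to be interrupted

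*Protocol*

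**What the plan says.** Both instructions stand in Protocol Section 4.5.3.2, Prior and Concomitant Medications.

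The paragraph on QT-prolonging medication gives as an example "the initiation of macrolides or fluoroquinolones in case of a lower respiratory tract infection". For that situation it says "IMP can be interrupted as evaluated by the investigator after clinical assessment" of the subject's profile, including baseline QTcF and its change over time. It then provides for the opposite choice: "If the investigator elects to continue IMP, additional monitoring will be performed", in a form left to the investigator's judgment.

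The paragraph on other concomitant medications, which covers CYP2C8, CYP3A4 and P-gp interactions, says "Antibiotics from the macrolide therapeutic class are excluded, unless they are used for the short-term treatment of a lower respiratory tract" and continues "infection with interruption of IMP, which is restarted as soon as possible after the completion of the treatment with macrolides". Its stated basis is that strong CYP3A4 inhibitors, with or without potent P-gp inhibition, "have shown that GLPG1690 exposure increased by 3 to 4 fold when coadministered". A general rule follows. Where benefit-risk calls for "administration of medication excluded from use during the study, IMP should be interrupted and restarted as soon as possible".

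Appendix 6 lists azithromycin, clarithromycin, erythromycin, roxithromycin and telithromycin as prohibited potent P-gp inhibitors, except under the condition set in Section 4.5.3.2. Appendix 5 lists clarithromycin and telithromycin again as strong CYP3A4 inhibitors, without that exception.

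The rescue medication paragraph, for worsening IPF such as an acute exacerbation, says "The decision to continue the IMP should be taken on a case-by-case basis by the investigator".

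**The concern.** For one drug class and one infection, interruption of IMP is optional in one paragraph and a condition of use in another. An investigator who turns to the QT paragraph finds the exact clinical situation named and an explicit route to continued dosing. That paragraph directs attention to QTcF and does not mention the exposure interaction that is the reason for the stricter rule. The subject could then take IMP together with an antibiotic that the protocol treats both as potentially QT-prolonging and as a prohibited inhibitor.

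Two things are at stake: subject safety during the antibiotic course, and consistent dosing across sites. Monitors could also classify the same conduct differently, as permitted under one paragraph or as a deviation under the other.

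**Working it through.** No plan figure needs reproducing, because the point depends on no alpha, power, effect size or sample size. The check is a comparison of the text.

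**1. Is the situation the same?** Yes. Both paragraphs concern macrolides for a lower respiratory tract infection. The QT paragraph names the class itself, and its continuation sentence follows directly without being limited to fluoroquinolones.

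**2. What does each paragraph allow?**

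| Site action | QT paragraph | Other-medications paragraph |
|---|---|---|
| Interrupt IMP, restart after the macrolide | permitted | required |
| Continue IMP with extra monitoring | permitted | not permitted |

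Interrupting satisfies both. Continuing satisfies one and breaches the other.

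**3. Does any text settle precedence?** None states it. Appendix 6 points to Section 4.5.3.2 by number, and that section holds both instructions. The only text there that sets a condition for macrolide use is the other-medications paragraph, so Appendix 6 supports the strict reading. It does so by reference and is not a separate rule. The general rule on excluded medication points the same way.

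**4. Does the rescue paragraph settle it?** No. It applies to worsening IPF, not to a lower respiratory tract infection as such.

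**5. Are fluoroquinolones affected?** No. The other-medications paragraph does not exclude them, and neither Appendix 5 nor Appendix 6 lists them. Discretion under the QT paragraph is coherent for that class.

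**6. Which drugs are involved?** Appendix 6 names 5 antibiotics under the condition. Of these, 2 of 5 are also in Appendix 5. None of the 5 is among the 6 drugs in Appendix 7, the non-exhaustive list to which the QT paragraph refers.

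**7. How large could the exposure effect be?** The documents do not say. Section 2.2.2 reports AUC 3-fold with itraconazole and 4-fold with voriconazole, and Cmax 1.4-fold with either, and calls the Cmax rise unlikely to be clinically significant. These drugs are azoles. No interaction study with any of the 5 antibiotics is reported, and the number and length of macrolide courses are not given.

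**The case against.** The strongest reply is that the paragraphs are cumulative. One manages QT risk and the other manages the interaction, so a drug carrying both risks must satisfy both, and permission on QT grounds does not lift an exclusion made on interaction grounds. On this reading the continuation sentence is meant for QT-prolonging drugs generally, such as fluoroquinolones, and Appendix 6 can refer only to the macrolide condition. This is a good account of what the authors probably meant, and it stands as such. It does not remove the difficulty: the QT paragraph uses macrolides as its own example and then provides for continuing, and nothing tells the reader that a second, stricter test applies.

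The second reply is that safeguards exist, and this also stands. Section 4.5.3.2 strongly advises consulting the CRO medical monitor or the sponsor's study physician before starting a QT-prolonging drug or a P-gp/CYP3A4 inhibitor. A macrolide qualifies on both grounds, so this is where a misreading would most likely be caught. Unscheduled visits (Section 6.2), extra safety assessments (Section 6.6), central reading of all ECGs (Section 6.6.5) and QTcF stopping rules (Section 4.5.4) add to it. The consultation is advised rather than required, and none of these says which paragraph governs.

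A reader might infer that a site following the QT paragraph would expose subjects to three or four times the intended GLPG1690 level. The documents do not support that. The figures come from azoles, and three of the five antibiotics (azithromycin, erythromycin, roxithromycin) are not on the strong CYP3A4 list.

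**Conclusion.** The conflict is real and minor. The QT paragraph permits what the other-medications paragraph forbids, for the same drug class and the same infection, and no text ranks the two. The stricter rule appears to be intended, and the safeguards keep the risk small. The conclusion rests on the plain wording of one section and needs no numerical assumption. The size of any exposure increase with a macrolide, and how often the situation arose, cannot be stated from the documents.

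A reader might also infer that the primary analysis is compromised. It is not: SAP Section 3.3 keeps all data in the full analysis set irrespective of IMP interruption, excluding only efficacy data after lung transplant. Nor does the rescue paragraph make continued dosing acceptable for an ordinary lower respiratory tract infection, since it is confined to worsening IPF.

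SAP Section 1 records that the studies were halted. That limits the practical effect of the conflict but does not make the instruction consistent.

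**What to change.** In the QT paragraph of Section 4.5.3.2, delete *macrolides or* so that the example covers fluoroquinolones only. Then add: *for macrolides, IMP must be interrupted; see Precautions with other concomitant medications*.

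Do not attach a rescue exemption to this sentence. The rescue paragraph stands as written. Appendix 11 counts infection-triggered events among acute exacerbations, so an exemption written into the macrolide rule would reopen continued dosing in infected subjects.

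Cost: a one-line wording change carried in the next protocol amendment, submitted to the ethics committees for approval before implementation as Section 10.4.1 requires, plus a site memo. No new procedure, visit or sample is needed, and discretion for fluoroquinolones is unchanged.

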4.5.3.3. Food and Beverage Restrictions

The use of St-John's Wort, a strong CYP3A4 inducer, is prohibited during the study.

Double-strength grapefruit juice is potentially a potent CYP3A4 inhibitor and therefore should be avoided during the study.

4.5.3.4. Other Prohibitions and Restrictions

Not applicable.

4.5.4. Treatment Discontinuation, Subject Withdrawal, and Study Termination

All subjects will continue on IMP until the last subject reaches 52 weeks into the study (Visit 12) (for details, please refer to Section 4.1 and to Section 6.1 "Specific study visits when the last subject reaches 52 weeks into the study (Visit 12)").

Subjects will be informed prior to clinical study entry that they are allowed to withdraw from the clinical study. At any time and for any reason, a subject's participation in the clinical study may terminate at his/her request, without prejudice to his/her future medical care. The subject

will be encouraged to share the reason(s) for withdrawal so this can be documented in the source documents.

Subjects who choose to withdraw from study participation will be asked if they are prepared to complete a last visit. In this case, either the EoST or EoSA visit should be performed. The subjects' vital status information will be collected at the time of the EoST/EoSA visit of the last subject who reaches 52 weeks in the study (Visit 12) according to national, ethical, and regulatory guidelines, and as per the subjects' confirmation in the signed main ICF. If the subject initially confirmed no vital status information to be collected, but reconsiders at the time of actual withdrawal of consent, the subject has to re-consent for this in writing.

Subjects who withdraw from the clinical study without contacting the clinical study center (lost to follow-up) should be contacted by the clinical study center so that their health status can be assessed and documented in the source documents. The clinical study center should make every effort to understand whether the subject is alive, including checking the medical records, contacting general practitioner or relatives, if necessary. All attempts must be documented in the source documents.

Subjects who discontinue IMP early (ETD), with the exception of patients who withdraw consent and patients lost to follow-up, will be encouraged to complete all following visits and evaluations as originally planned per protocol (see below, "Procedures in case of early treatment discontinuation (ETD)").

The sponsor has the right to terminate the clinical study at any time in case of safety concerns or if special circumstances concerning the IMP or the company itself occur, making further treatment of subjects impossible. In this event, the subjects, investigator(s), and relevant authorities will be informed of the reason for clinical study termination.

Discontinuation of IMP

Treatment with IMP will be discontinued by the investigator (preferably after discussion with the CRO medical monitor, who may consult and must inform the sponsor's study physician) for any of the following reasons:

- Life-threatening AE or a serious adverse event (SAE) that places the subject at immediate risk.
- Confirmed pregnancy: if a subject becomes pregnant during the study (to be confirmed by local serum pregnancy test; central measurement will also be performed), the IMP has to be stopped immediately and the subject has to be followed up until birth or otherwise termination of pregnancy. The subject needs to be unblinded immediately and repeat counseling on birth defect risk must be offered in case she was on active drug.
- Arrhythmia or conduction abnormality, including but not limited to prolonged QTcF, where the severity is categorized as Common Terminology Criteria for Adverse Events (CTCAE) Grade 3 or higher.
- An increase for QTcF of >60 ms from baseline (Visit 3) or QTcF >500 ms at any ECG recording (any recording of triplicate ECG or single ECG) needs to be confirmed by an ECG recording as soon as possible from the original abnormal recording at the same visit. If the abnormal recording is discovered after the visit, the recording should be confirmed as soon as possible. In case of an abnormal ECG on both of these two recordings is confirmed, the investigator needs to send an immediate alert to the central reader for confirmation as well as to the CRO medical monitor (as per study contact list) or sponsor's

study physician (if the former is not available). If the ECG abnormality is before IMP intake, IMP administration will be withheld until the central reader has reviewed the ECG registration. In case of confirmation of the ECG abnormality, IMP will be discontinued for this subject. Only in case a response of the central reader is not available within the timeframe of the visit, the investigator can proceed to discontinue the treatment of the subject.

If a normal QTcF is reported during the visit, but the central cardiologist reports it as abnormal (any of the two criteria above), then the IMP should be discontinued as soon as possible.

- Increase in LFTs (also see [Appendix 9](#)):
 - At Visit 3 immediately after randomization: test results will only be available after the first IMP intake. If the subject meets the exclusion criteria for AST, ALT, total bilirubin, and GGT, then treatment with IMP will be discontinued.
 - Any other visit:
 - AST or ALT $\geq 8xULN$
 - AST or ALT $\geq 3xULN$ with signs of severe liver damage (i.e. with the appearance of fatigue, nausea, vomiting, right upper quadrant pain or tenderness, fever, rash and/or eosinophilia [$>5\%$], and/or total bilirubin $\geq 1.5xULN$ or INR >1.5)
 - AST or ALT $\geq 3xULN$ for more than 2 weeks
 - AST or ALT $\geq 3xULN$ during re-escalation
- Clinical laboratory test suggestive of cholestasis with total serum bile acid levels $>3xULN$ on a sample taken in fasted state (at least 8 hours fasted). If the routine random or postprandial total serum bile acid sample is $>3xULN$, then the subject should have a fasted sample taken within 1 to 5 days. The results of this test will determine whether the subject should discontinue IMP or not.
- Chronic (defined as: anticipated to be administered for more than 3 months) use of concomitant medication not permitted during the study.
- Closing of the study by the sponsor or regulatory authorities.
- Wish of the subject to stop taking IMP.

For a subject having:

- AST or ALT $\geq 8xULN$
- AST or ALT $\geq 3xULN$ with signs of severe liver damage (i.e. with the appearance of fatigue, nausea, vomiting, right upper quadrant pain or tenderness, fever, rash and/or eosinophilia [$>5\%$], and/or total bilirubin $\geq 1.5xULN$ or INR >1.5)

the following steps will need to be performed by the investigator.

- The site should immediately contact the subject and require the subject to discontinue IMP immediately. The subject should be asked to return to the site within a 48-hour window from awareness of the result.
- An assessment of other concomitant medications and SoC should be made. The investigator should consider whether it is in the best interest of the subject to interrupt concomitant medications and SOC treatment.

- A detailed history including relevant information on alcohol use, recreational drug use, supplement consumption, any herbal remedies, family history, sexual history, travel history, history of contact with a jaundiced subject, surgery, occupational history, blood transfusion, history of liver or allergic disease, and any other potential causes of a liver insult should be collected.
- A detailed assessment of the subject's clinical condition and repeat laboratory tests for LFT, including albumin, creatine kinase, total bilirubin (direct and indirect), GGT, INR and alkaline phosphatase should be done
- Further testing for Hepatitis A, B, and C, and for autoimmune hepatitis should be done. Other causes of viral hepatitis (CMV or EBV etc) should be excluded. Liver imaging should be considered.
- Referral to a hepatologist or gastroenterologist should be considered.
- All these cases should be reported as SAEs.

Every effort should be made to keep subjects in the study and on treatment. However, the investigator can consider stopping treatment with IMP, preferably after consultation with the CRO medical monitor (as per study contact list) or sponsor's study physician (if the former is not available), in case of concerns about the subject's safety, major protocol noncompliance, serious or severe AEs or worsening of the disease condition, which in the investigator's opinion needs an alternative treatment approach not being covered in the clinical study (e.g. rescue medication).

– At Visit 3: as the blood sample is taken before first IMP intake and the results are only available after first IMP intake, the investigator needs to justify continuation of IMP in writing for abnormal results (based on the exclusion criteria) for:

- Creatinine clearance
- Hb

The reason(s) for stopping the IMP will be documented in the CRF.

Procedures in case of early treatment discontinuation (ETD)

Subjects who discontinue IMP early will complete an ETD visit. They will be encouraged to complete all following visits and evaluations as originally planned per protocol (i.e. including an EoSA visit when the last subject reaches 52 weeks into the study [Visit 12]). The subject will be informed about this at signing of the ICF.

In particular, the subject will be requested if at all possible to attend:

- the first scheduled visit after their Early Treatment Discontinuation (ETD)
- The Week 26 visit (if not done before IMP discontinuation)
- the Week 52 visit (if not done before IMP discontinuation)
- after Week 52, visits every 24 weeks up to EoSA, as described in Section 6.11.2

An ETD visit will be scheduled as soon as possible from the day of early discontinuation of IMP. In case the subject discontinues IMP on a scheduled visit, that visit should be completed and, in addition, the assessments from the ETD visit that are not part of the scheduled visit

should be performed. If the subject is not able or not willing to come back for an ETD visit, the investigator will contact the subject by phone, and if the subject has agreed to this in the ICF, may consult the subject's medical record and/or contact the subject's general practitioner or relatives, if necessary, to obtain the needed information.

